1. PURPOSE OF STUDY

Connect for Caregivers is a mixed method intervention development pilot study. The purpose of the study is to develop and pilot test a single session behavioral intervention to help caregivers gain understanding of the importance of increasing social connectedness, awareness of their personal barriers to connectedness, and knowledge of local resources for promoting connectedness. The specific aims of this mixed method study are:

Aim 1 To characterize caregivers' understanding of their experiences of social connectedness and of their perceptions of barriers to social connectedness, including which barriers are most common, most problematic, and most difficult to change.

Aim 2 To use information provided by caregivers (in Aim 1) to develop a card sort discussion prioritization tool (*Connect for Caregivers*) that will systematize and routinize a process whereby caregivers and interventionists can collaboratively identify and prioritize personalized intervention targets for promoting connectedness.

Aim 3 To investigate whether *Connect for Caregivers* (a card sort discussion prioritization tool combined with personalized education and resources) is associated with a signal for efficacy for changing connectedness.

This submission is for conducting Aim SA3, the final phase of the study, as approved in the original study Protocol.

2. BACKGROUND AND RATIONALE

Older caregivers for family members with Alzheimer's disease or related dementia (ADRD) are at risk for social disconnectedness that impacts health and quality of life. Social connectedness represents an untapped intervention target to improve caregiver well-being and health. Caregivers who report high social connectedness appear to be buffered from high caregiving burden because they perceive more positive aspects of caregiving. Barriers to connectedness among caregivers are numerous, varied, and dynamic. Current caregiver interventions effectively improve outcomes for the family

member with dementia and reduce caregiver burden, but do not improve connectedness for the caregiver. Other interventions (e.g., caregiver support groups) have not been tested with regards to connectedness. The evidence base for strategies to promote connectedness is extremely limited. Promising interventions are multifaceted, intensive, and/or involve significant time out of the home, rendering them infeasible for most caregivers. There are no evidence-based interventions for promoting connectedness in older caregivers for individuals with ADRD.

3. ADMINISTRATION ORGANIZATION

Caregiver interviews will be conducted in the subject's home or convenient location identified by the subject. Due to the COVID-19 pandemic, part SA2 will be conducted by ZOOM and since we will use video and audio, caregiver subjects will need to have a stable internet connection to participate. The focus group will be conducted via ZOOM.

4. STUDY DESIGN

This is a mixed method intervention development study using semi structured interviews (SA 1a and 2) and a focus group (SA 1b) to develop and refine a psycho-behavioral intervention that we will then pilot test (SA 3) using a non-randomized single arm prepost approach.

Study outcomes/endpoints

Aim 3: To investigate whether Connect for Caregivers—a card sort discussion prioritization tool combined with personalized education and resources—is associated with a signal for efficacy for changing connectedness. We will be conducting AIM SA3 in this phase of the study, as approved in the original study Protocol.

- Outcome 3a: A **non-random sample of caregivers (n=5)** will complete the Connect for Caregivers tool with a research assessor, including discussing psychoeducational materials on the benefits of social connectedness, completing the card sort to identify personal barriers to connectedness, and reviewing personalized community resources to address those barriers. Using semi-structured interviews, they will provide feedback on the experience of the intervention, including ease of completing it and potential utility as well as the extent to which they experienced the SDT mechanisms of: autonomy, competence, and relatedness while completing the tool and after completing it.
- Outcome 3b: Participants will also complete quantitative measures of their motivation to increase social connectedness via self-report measures that assess mechanisms posited by Self-Determination Theory (i.e., autonomy, competence, relatedness). Participants will complete these measures at their initial screening interview and again after completing the Connect for Caregiver intervention.

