9. STUDY PROCEDURES

Caregiver Subjects: The card sort intervention will be conducted by a trained research assistant (RA). The intervention will be conducted via ZOOM, audio-recorded, and typically last between 45-60 minutes. Interview questions will focus on (1) how participants characterize social connectedness and activities they use to connect, (2) social connections that are important/meaningful to them, (3) what makes social connections easier and more difficult (including barriers), (4) how their social connections may have changed with the caregiver role, (5) how or whether they prioritize social connectedness in their day to day lives, and (6) the advice they would give to new caregivers about maintaining or improving social connections. We will use a laddered technique with early questions designed to be minimally intrusive and deliberately broad to allow participants to focus on the experiences of social connection important to them. Later questions will be built off the earlier questions and probe for detail and specific examples of participants' unique experiences with social connectedness. The semi-structured interviews will be audio recorded so that the full conversation can be transcribed for later analysis, and subjects will be informed of this before discussion begins. No identifying information (for example, subject names, or other details shared during the discussion) will be included in the transcript. The audio recording will be transferred from the recording device to a secure computer in the School of Nursing, after which the recording will be deleted from the recording device. The de-identified electronic version of the transcript will remain on the School of Nursing's secure computer where it will be accessible only to the study PI and project team members. For Aim SA3, new measures will be used and are based on the work completed in AIMS SA1 and SA2.

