19. STATISTICAL ANALYSIS PLAN

Testing the 'Connect for Caregivers' discussion prioritization tool: Aim 3 involves a pilot test of the Connect for Caregivers discussion prioritization tool with a sample of caregivers who report disconnectedness (n=5). Caregivers will receive the psychoeducation materials on connectedness (delivered by research staff), complete the card sort task to identify personal barriers to connectedness, and received personalized community resources to address their identified barriers to connectedness. Using the methodology described in Aim 1 for semi-structured interviews, caregivers will provide feedback on the experience of the intervention, including ease of completing it and potential utility. Participants will also complete quantitative measures of their motivation to increase social connectedness via self-report measures that were developed to test mechanisms posited by Self-Determination Theory that we have used with success in prior studies with social connectedness interventions (i.e., Perceived Competence Scale and Perceived Autonomy Scale). Participants will complete these measures at their initial screening interview (as described in the STAR Core Battery above) and again after completing the Connect for Caregiver intervention. We will use descriptive statistics to compare changes in mean scores pre and post completion of the tool.

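### Aim 3 asks about change in connectedness, but the specified pre/post outcomes measure motivation and no connectedness measure is scheduled after the intervention

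*Combined protocol and SAP*

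**What the plan says.** Sections 1 and 4 both give Aim 3 as finding out whether the tool "is associated with a signal for efficacy for changing connectedness". Section 4 lists two outcomes under it.

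- **Outcome 3a** is a semi-structured interview about how easy and useful the tool was, and about "the extent to which they experienced the SDT mechanisms of: autonomy, competence, and relatedness".
- **Outcome 3b** is self-report of motivation to become more connected, using measures of "mechanisms posited by Self-Determination Theory (i.e., autonomy, competence, relatedness"), taken at the screening interview and again after the intervention.

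Section 19 repeats the motivation construct: "Participants will also complete quantitative measures of their motivation to increase social connectedness via self-report measures". The scales it names are the "Perceived Competence Scale and Perceived Autonomy Scale", with the first administration at screening "as described in the STAR Core Battery above". The analysis is one sentence: "We will use descriptive statistics to compare changes in mean scores pre and post completion of the tool".

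Two other places bear on the point. Section 6, inclusion criterion 3, uses the UCLA Loneliness Scale Short Form under the label of social connectedness, assessed at the HARP screening assessment. Section 9 says: "For Aim SA3, new measures will be used and are based on the work completed in AIMS SA1 and SA2". It does not name those measures.

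**The concern.** Wanting to be more connected, or feeling competent and autonomous about it, is not the same as being more connected. The aim names the second, and the specified data address the first. If the motivation scores rise, the natural report under Aim 3 is a signal of efficacy on connectedness, and that conclusion would not follow from what was measured.

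Aim 3 is the only aim being carried out in this phase, so the mismatch decides what the pilot may claim and what a later trial could cite from it. Section 2 justifies the study partly on the ground that existing caregiver interventions either do not improve connectedness or have not been tested on it. As specified, this pilot would leave the new tool untested on it too.

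**Working it through.** The documents give no derived figure to reproduce: n=5 is stated without an effect size, standard deviation, alpha or power. The check is to list each candidate measure with its construct and time points.

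| Measure | Where | Construct | Before | After |
|---|---|---|---|---|
| Interview feedback | Section 4, Outcome 3a | Ease, usefulness, experience of SDT mechanisms | No | Yes |
| Perceived competence scale | Section 19 | Motivation / SDT mechanism | Yes | Yes |
| Perceived autonomy scale | Section 19 | Motivation / SDT mechanism | Yes | Yes |
| Relatedness | Section 4, Outcome 3b | Motivation / SDT mechanism | Yes, no scale named | Yes, no scale named |
| UCLA Loneliness Short Form | Section 6 | Connectedness, as an entry criterion | Yes | Not stated |
| New SA3 measures | Section 9 | Not stated | Not stated | Not stated |

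Counts from the table:

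- Named connectedness measures with a post-intervention time point: 0.
- Connectedness scales among the pre/post scales named in Section 19: 0 of 2.
- SDT mechanisms in Outcome 3b with a scale named in Section 19: 2 of 3. Relatedness is the one without, so Sections 4 and 19 do not agree.

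The battery cited in Section 19 is not in the text available for review, and its absence is not held against the plan. Section 19 cites it for the motivation measures at screening, so the citation does not in itself set up a connectedness outcome after the session.

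A separate question is whether adding a connectedness scale would rescue the efficacy wording. With n=5 it would not:

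- Exact two-sided sign test, all 5 changes in one direction: 2 × 0.5^5 = 0.0625.
- The same test with 4 of 5 in one direction: 2 × (5 + 1) × 0.5^5 = 0.375.
- Half-width of a 95% interval for the mean change: t(0.975, 4 df)/√5 = 2.776/2.236 = 1.24 standard deviations of the change scores.

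The plan proposes no test or interval. These figures do not measure the mismatch; they only show the limit of the second remedy.

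**The case against.** The strongest reply has four parts.

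- **Relatedness is close to connectedness**, and Outcome 3b measures it before and after. This stands in part: it is the nearest construct listed. But Section 4 treats it as a mechanism of motivation and Section 19 gives it no scale, so it cannot carry the aim as written.
- **A connectedness measure may sit in the cited battery or among the new SA3 measures.** That is possible, and the finding is limited to what the text specifies. Neither reference is described as a post-intervention connectedness outcome. If such an outcome exists, a sentence in each of Sections 4 and 19 would close the point.
- **This is a minimal-risk development pilot** that seeks only a signal, plans descriptive statistics and lists its outcomes openly. Section 1 describes the session's purpose as understanding, awareness and knowledge, so measuring proximal mechanisms after one session is reasonable. This is a fair defence of the outcomes, but not of the aim. Calling the result a signal weakens the strength of the claim and leaves its subject unchanged. That the result would be over-read is a forecast, but it is what the aim's wording invites.
- **The missing relatedness scale and the unnamed new measures are separate documentation gaps.** That is right. They should be repaired, but the finding does not rest on them.

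**Conclusion.** The concern holds. The plan asks about change in connectedness and specifies data on motivation: no connectedness measure has a stated post-intervention time point, and neither of the two named pre/post scales measures connectedness. This is more than missing detail, because carrying out the plan exactly as written would not answer its only active aim.

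The conclusion assumes that the cited battery and the unnamed new measures do not define a post-intervention connectedness outcome; nothing in the text says that they do. No safety issue follows. What is at stake is the conclusion the pilot may draw, so the aim and outcomes should be brought into line before results are reported.

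**What to change.** **Preferred.** Restate Aim 3 in Sections 1 and 4 as feasibility, acceptability and pre/post change in motivation (SDT mechanisms), drop the reference to efficacy for connectedness, and align Section 19. Either name the relatedness scale in Section 19 or remove relatedness from Outcome 3b. Name the new measures mentioned in Section 9. The cost is wording, possibly with a protocol amendment (an assumption, since the aim is described as already approved), and a less ambitious claim.

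**Alternative, if connectedness stays in the aim.** Name a connectedness measure with a post-intervention time point. The UCLA Loneliness Short Form is the obvious candidate because it is already used at screening. Take it just before the session, since a screening score used to select participants is a poor baseline, and again at a stated interval long enough for connectedness to change. List the five individual changes descriptively, and state that five participants without a control cannot support an efficacy conclusion. The cost is a few minutes of questionnaire twice per participant, and possibly one extra contact: Section 14 refers to three parts of SA3, but their timing is not described.

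Neither option changes the sample size, the eligibility criteria or the intervention.

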5. SUBJECT POPULATION

We will enroll approximately **5 subjects**, who are **caregivers** (age 50 or older) for a community-dwelling family member with ADRD, living with (or in close proximity to) the family member with dementia. Caregivers will be recruited from the IRB approved

Health Aging Research Program (HARP) Population Study (RSRB00068059) (see III-d Recruitment Procedures). Care managers will be recruited from Lifespan of Rochester.

Gender, Age, Racial, and Ethnic Origin of Subjects:

Caregivers in the US are more likely to be women (67%); Caregivers are also more likely to be white, non-Hispanic (67%), while 10% are African American and 8% are Hispanic. Using the 2018 Alzheimer's Disease Facts and Figures along with our local demographic distributions, we plan to target 25% minority and 67% women enrollment. We will proactively recruit minority participants (including targeting men for enrollment, as they represent the gender minority in the caregiver population) using best practices for minority recruitment, including working with providers serving minorities; collaborating with community gatekeepers; tailoring the recruitment materials to the culture and education level in inner city populations.

Procedures for assignment to a study group: Specific Aims 1 and 2 are descriptive. For Aim 3, all subjects will receive the intervention. Aim 3 is a single-arm pilot of the newly developed intervention, *Connect for Caregivers*. For Aim SA3, the originally approved N of 5 subjects will be enrolled. No additional subjects will be enrolled.

6. INCLUSION AND EXCLUSION CRITERIA

Caregiver Inclusion criteria (assessed at the HARP Population Study RSRB00068059, screening assessment):

- 1) Caregiver (age 50 or older) for a community-dwelling family member with ADRD, living with (or in close proximity to) family member with dementia.
- 2) Elevated caregiving distress: Above population mean (>11) on 10-item Perceived Stress Scale (PSS-10) and/or at least moderate caregiver strain (score >= 5) on the Modified Caregiver Strain Index (MCSI).
- 3) Social connectedness: UCLA Loneliness Scale: Short Form score of equal to or greater than 6 (n=10; Short Form score of 3-5, n=10).
- 4) Able to provide informed consent to participate in the research study.
- 5) For phase SA2, a stable internet connection for using Zoom video and audio.

Caregiver Exclusion criteria (assessed at the HARP screening assessment):

- 1) Non English speakers because our primary community partner agency (Lifespan) cannot currently accommodate non-English speaking clients.
- 2) Current problem drinking on the AUDIT-C (score of 5 or greater indicating exclusion).
- 3) Current non-alcohol psychoactive substance abuse (MINI Neuropsychiatric Interview), psychotic disorders (current and lifetime, MINI), bipolar disorder (MINI), and current mood disorder with psychotic features (MINI).
- 4) Significant cognitive impairment (MOCA <22) and those with hearing problems that preclude completion of interviews will be excluded.

Vulnerable Subjects: Individuals who are 50 years of age and older with social risk factors for poor mental and physical health outcomes will be included. The results of this study will inform future research and clinical interventions aimed at improving mental health treatment for older caregivers.

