7. RECRUITMENT METHODS

Caregiver subjects will be recruited via the IRB approved HARP Population Study (RSRB00068059), a research registry run by the current study's Investigators. In compliance with procedures of the Population Study protocol, subjects of the Population Study consent to allow HARP Population Study researchers to share subjects' identifiable data (both name and contact information) with investigators conducting HARP research at the University of Rochester; in addition, they consent to allow their data collected as part of the Population Study to be included in their research record for subsequent HARP studies they participate in, including the current study. All eligible participants will be provided with a study brochure, at their in-person screening visit and given information about the study.

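### Do the two loneliness bands with quotas of 10 each in inclusion criterion 3 leave it unclear who may enter the five-person Aim 3 pilot?

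*Combined protocol and SAP*

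**What the plan says.** Section 1 states that the submission is for Aim 3. Section 5 fixes the size: "For Aim SA3, the originally approved N of 5 subjects will be enrolled. No additional subjects will be enrolled". Section 4 describes the participants as a "non-random sample of caregivers (n=5", and section 19 as "a sample of caregivers who report disconnectedness (n=5".

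Section 6 holds the only list of caregiver eligibility criteria in the text. Its criterion 3, on social connectedness, reads "UCLA Loneliness Scale: Short Form score of equal to or greater than 6 (n=10; Short Form score of 3-5, n=10". It names no phase, whereas criterion 5 in the same list does: "For phase SA2, a stable internet connection for using Zoom video and audio". The caregiver criteria are "assessed at the HARP Population Study RSRB00068059, screening assessment", and section 7 says of registry participants that "they consent to allow their data collected as part of the Population Study to be included in their research record".

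The only other mention of disconnectedness is in section 2, where older caregivers "are at risk for social disconnectedness that impacts health and quality of life". It is not defined there either. The UCLA scale is named only in criterion 3.

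**The concern.** Someone screening for Aim 3 from section 6 alone meets two adjoining bands and two quotas. The quotas cannot be met with five people. If they belong to an earlier phase, the 3-5 band may belong to it too, and the text does not say. One screener could accept any score of 3 or higher and another only 6 or higher.

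Section 19 gives the sample a label that implies a threshold but does not state one. If caregivers scoring 3-5 were enrolled and the result reported under that label, the description might not fit the people behind the means. Aim 3 looks for early evidence of an effect from a single-arm pre/post comparison. Each of the five participants contributes one fifth of the mean, so a reader would want to know where they started.

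**Working it through.** **Inputs.** Section 6, criterion 3: score of 6 or more, n = 10; score of 3-5, n = 10. Sections 4, 5 and 19: Aim 3 sample of 5. The plan states no alpha, power, effect size or standard deviation, so there is no sample-size calculation to reproduce.

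**Quotas against the sample.**
- Total: 10 + 10 = 20, and 20 / 5 = 4 times the sample.
- One band: 10 / 5 = 2 times the sample.
- Scaled in proportion: 5 × 10 / 20 = 2.5 per band, not a whole number.

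The quotas therefore cannot apply to Aim 3, in full or in proportion.

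**Scores admitted.**
- Both bands eligible: {3, 4, 5} together with {6 and above} = {3 and above}.
- Main clause only: {6 and above}.
- Difference: {3, 4, 5}, three integer scores.

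The documents give neither the range of the scale nor a distribution of scores. If the lowest possible score were 3 (an assumption), the two bands together would exclude nobody. How many of the five would score 3-5 cannot be estimated.

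**What remains defined.** Age, caregiver role and living arrangement, the distress thresholds (PSS-10 above 11 and/or MCSI of 5 or more), capacity to consent and all the exclusions are stated in section 6. The number enrolled is stated in section 5. Only one element of eligibility is in question, over three scores.

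**What depends on it.** Outcome 3a in section 4 is interview feedback. Outcome 3b is self-reported motivation, which section 19 measures with the Perceived Competence Scale and the Perceived Autonomy Scale and summarises by descriptive comparison of pre and post means. The UCLA score is not named as an outcome, covariate or stratifying factor. No hypothesis test, decision threshold or precision statement uses it. Changing the cut-off from 3 to 6 could change who is enrolled, but not what is computed.

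**Where the quotas probably come from.** The text keeps other material from earlier phases: home interviews and a focus group in section 3, care manager recruitment in section 5, and the care manager focus group in section 13. Section 5 also points to a recruitment section III-d, and section 19 to a core battery said to be described above; neither appears in the supplied text. Quotas of 10 and 10 fit this pattern of carried-over wording, although no passage names the phase they came from.

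**The case for a change.** The strongest case for a change is that an eligibility rule should not have to be inferred. Criterion 5 shows that the authors labelled phases when they meant to, so the absence of a label on criterion 3 can be read as applying it to Aim 3. If the bands are leftovers, Aim 3 has no expressly stated loneliness rule. Section 19 does not supply one, and equating disconnectedness with a score of 6 or more is a guess, however reasonable. A clarifying phrase would cost almost nothing.

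Much of this stands: the link between the two sections is not written down, and the quotas are out of place. It does not establish a contradiction, because nothing in the documents says that a caregiver scoring 3-5 is not disconnected; the section 19 label could be true on either reading. Nor does it identify a bias, in direction or size.

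The possible remedies also show that this is not a statistical error. One would restrict entry to 6 or more. The other would admit 3 or more and drop the section 19 description, which alters the stated target population. Nothing in the analysis favours either. Listing each participant's loneliness score beside the pre/post change would be a preference, and publishing it for five people would have to be checked against the anonymity commitment in section 16.

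**Conclusion.** The observation is accurate but calls for no change to the plan. It combines leftover quota wording with an unstated link between a label and a scale. The discrepancy is 20 quota places against five participants, and the open question covers three integer scores on one criterion. The enrolled number, the other criteria and the planned analysis are unaffected.

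A sensible analyst would read criterion 3 by its main clause, a score of 6 or more, alongside the section 19 description, and would disregard quotas that cannot fit. If caregivers scoring 3-5 were enrolled, the screening scores could be summarised so that the sample is described as it was.

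This rests on two points. First, the Aim 3 quantitative analysis remains descriptive, as section 19 states. Second, the screening score is available to the study team, as sections 6 and 7 together indicate. Whether the originally approved protocol, to which sections 1 and 4 refer, states the Aim 3 cut-off cannot be determined from the supplied text.
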